## 16. STATISITICAL CONSIDERATIONS

Statistical analysis will be performed in collaboration with [name], the Director of the University of Arizona Cancer Center Biometry Shared Service. The primary outcome is the change in the fatigue score between radiation days 15 (day prior to IP initiation) and 26 (day after IP completion) in the dexamethasone versus placebo patients as measured by the Functional Assessment of Chronic Illness-Fatigue (FACIT-F) 13-item fatigue subscale. Secondary endpoints include the QoL score as measured by the FACIT-F 40-item total score, and the total days and cause of treatment interruption. Randomization will be stratified by tumor location and treatment type (radiation alone versus radiation plus systemic therapy). Analysis of the continuous endpoints (change in FACIT-F fatigue subscale and change in FACIT-F total score) will be performed using a two-sample independent t test comparing the dexamethasone versus placebo patients. Analysis of the total days of treatment interruption will be performed using a Wilcoxon Rank Sum Test, since the number of days may not be normally distributed. Alternatively, the proportion of patients with any treatment interruptions will be compared using a Fisher's Exact Test.

The sample size of 40 patients per group was chosen based on the previous study of Yennurajalingam et al. in advanced cancer patients with at least three cancer-related fatigue symptoms. They observed a mean improvement in the FACIT-F fatigue score of 9.0 (standard deviation = 10.30) in the dexamethasone treated group versus a mean improvement of 3.1 (standard deviation = 9.59) in the placebo group. We chose a one-sided statistical test (at the alpha = 0.05 level) as dexamethasone will only be recommended in our patient population if it improves cancer-related fatigue. Based on these considerations, 36 patients per group will provide 80% statistical power. We rounded the necessary sample size up to 40 patients to allow for the possibility of up to a 10% drop-out of patients from their radiation therapy between days 16 and 26.

Exploratory analyses will profile the change in the FACIT-F fatigue subscale and FACIT-F total score across the entire radiation therapy course (measured at baseline screening, on RT days 5, 10, 15, 20, 25, 26, and 30, and 60 day follow-

up) separately for the dexamethasone versus placebo treated patients. Descriptive statistics (mean, medians, standard deviations) will be computed separately for each treatment group at each time point.

The primary safety endpoint is random plasma glucose levels measured on radiation therapy day 15, 20 and 25. Treatment will be terminated in patients if the RPG  $\geq$  250 mg/dL. The FACIT-F questionnaire will continue to be administered per study protocol even if dexamethasone or placebo treatment is terminated. The proportion of patients with treatment terminations will be compared between the two groups using a Fisher's Exact Test. Adverse events will be summarized using CTCAE criteria for each treatment group separately.

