## 26. STUDY SCHEDULE

	Baseline screening	RTD1	Weekly	RTD15	RTD16	RTD20	RTD25	RTD26	RTD30 **	Last Day of RT	30 & 60 day F/U
			During RT (+/- 2 RT Days)								
Informed Consent/Enrollment	X										
Medical history (1)	X										
Physical exam and KPS (2)	X								X **	X	X
Assess recent/concurrent meds (3)	X										
Hematology (4)	X										
Tumor info and treatment (5)	X										
Registration	X										
Randomization	X										
FACIT-F total QoL (6)	X		X	X 		X	X		X	X	X
Dispense Medication				X							
Investigational Product (7)					X			X 12			
Pill Diary				X				X 12			
Observation Form (11)				X				X		X	X
RPG fingerstick (8)				X		X	X			X 	X 
Adverse event evaluation		X	X	X		X	X		X	X	X
RT treatment interruptions										X	

1 = Medical history will include demographics (this can be done within the last 60 days prior to registration as part of standard of care)

2 = All physical exams to include vitals (BP, pulse, temperature, weight) (this can be done within the last 60 days prior to registration as part of standard of care)

3 = Review current medications including corticosteroid, psychostimulant, and systemic cancer treatments in past 30 days

4 = Hematology to include Hgb and ANC within the last 90 days as part of standard of care, or after consenting, but prior to first treatment

5 = Confirmation of cytologic or histologic evidence of HN or non-small cell lung cancer

6 = QoL survey, 27 questions (completed ± 2 RT days from scheduled time point)

7 = Start IP and take for 14 consecutive days, unless IP stopped due to elevated RPG

8 = RPG fingerstick (completed ± 2 days from scheduled time point). IP will be stopped if RPG ≥ 250

9 = Survey to be completed the day before IP initiation

10 = RPG per physician discretion

27. GLOSSARY: Not applicable

28. DEFINITIONS: Not applicable

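### The primary endpoint is scored on RT day 26, but the schedule's FACIT-F row, Section 9.6 and Section 8.2 do not call for a day-26 form, and its ±2 window reaches back into dosing

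*Combined protocol and SAP*

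**What the plan says.** Section 16 sets the primary outcome as the "change in the fatigue score between radiation days 15 (day prior to IP initiation) and 26 (day after IP completion"), dexamethasone against placebo. It treats days 25 and 26 as separate assessments, listing surveys "on RT days 5, 10, 15, 20, 25, 26, and 30". On early termination it adds: "The FACIT-F questionnaire will continue to be administered per study protocol even if dexamethasone or placebo treatment is terminated".

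Section 7.1 agrees with Section 16. It asks for both the 13-item and the 27-item forms at each time point, including RT days 15, 25 and 26, each with a ±2 day window. It describes day 15 as the day before IP starts. It also requires the day-26 survey after an early IP stop for any reason, so that the patient can enter the intention-to-treat analysis.

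The other collection instructions differ:
- **Section 26, schedule.** The row "FACIT-F total QoL (6") has no mark under RTD26. The row "Observation Form (11") does.
- **Section 26, footnotes.** Footnote 6, on the FACIT-F row, reads "QoL survey, 27 questions (completed ± 2 RT days from scheduled time point"). Footnote 9, on the RTD15 mark, reads "Survey to be completed the day before IP initiation".
- **Section 9.6.** For the same intention-to-treat purpose, early stoppers complete surveys on RT days 25 and 30, and on the last day if RT runs past 30 treatments, within ±2 RT days.
- **Section 8.2.** After a stop for elevated random plasma glucose (RPG), surveys are weekly during RT and then at 30 and 60 days.

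**The concern.** The primary analysis needs one form in a defined place: after the last IP dose, at RT day 26. Staff working from the schedule, 8.2 or 9.6 would collect an RT day 25 or weekly form and might collect none for day 26. The primary value would then be missing, or an analyst would have to put a neighbouring form in its place. For a patient still taking IP with no missed fraction, the day-25 form is an on-drug score, while the endpoint is defined as a score taken the day after IP completion.

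The instructions conflict most for patients who stop IP early. One stopping rule (RPG of 250 mg/dL or more) responds to an effect that Section 4.2 describes as a known consequence of corticosteroids. Gaps or substitutions therefore need not be balanced between arms.

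**Working it through.** **1. The plan's sample size.** Inputs from Section 16: mean improvements 9.0 (SD 10.30) and 3.1 (SD 9.59), one-sided alpha 0.05, power 80%.
- Difference = 9.0 - 3.1 = 5.9. Pooled SD = √((10.30² + 9.59²)/2) = 9.95.
- n per group = 2 × (1.645 + 0.842)² × 9.95² / 5.9² ≈ 35.2, so 36. Noncentral-t power at 36 is 0.801.
- 36 / 0.9 = 40.

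The stated 36 and 40 reproduce. Nothing below changes them.

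**2. The schedule rows side by side (Section 26).**

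| Row | RTD15 | RTD16 | RTD20 | RTD25 | RTD26 | RTD30 | Last day |
|---|---|---|---|---|---|---|---|
| FACIT-F | X (fn 9) | blank | X | X | blank | X | X |
| Observation form | X | blank | blank | blank | X | blank | X |

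The IP and pill diary rows also have entries under RTD26, so the column is in use and the FACIT-F blank does not look like a lost column.

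**3. Where RT days fall on the IP calendar.** Inputs: RT Monday to Friday (2.4); IP from RT day 16 for 14 consecutive days (8.3); no missed fraction. Fourteen days contain ten weekdays, so RT 16 + 10 = RT 26 falls on IP day 15, the first day off drug, for every starting weekday.

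| Weekday of RT 16 | RT 17 | RT 24 | RT 25 | RT 26 | RT 28 |
|---|---|---|---|---|---|
| Mon | 2 | 11 | 12 | 15 | 17 |
| Tue | 2 | 11 | 14 | 15 | 17 |
| Wed | 2 | 13 | 14 | 15 | 17 |
| Thu | 2 | 13 | 14 | 15 | 19 |
| Fri | 4 | 13 | 14 | 15 | 19 |

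(Cells are IP days; 1-14 are on drug.)

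**4. The day-26 window.** Section 7.1 says ±2 days. Footnote 6 and the Section 26 column header say ±2 RT days.
- *RT days:* RT 24-28. RT 24 and 25 are IP days 11-14, on drug for a patient still taking IP.
- *Calendar days:* 15 ± 2 = IP days 13-17, of which 13-14 are on drug. A Monday start has no RT visit on those two days (they are a weekend), a Tuesday start has one (RT 25), and the other starts have two.

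**5. Overlap with day 25.**
- *RT days:* day 25 covers RT 23-27 and day 26 covers RT 24-28, so they share RT 24-27.
- *Calendar days:* for Tuesday to Friday starts, day 25 covers 14 ± 2 = IP days 12-16, which shares IP days 13-16 with day 26. For a Monday start the shared days are only the weekend.

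No section says which form supplies the primary value.

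**6. The baseline window.** Read literally in RT days, 15 ± 2 is RT 13-17. RT 16 is IP day 1, and RT 17 is IP day 2 (4 for a Friday start). In calendar days, a Monday start reaches neither and a Friday start reaches only RT 16. The descriptions of day 15 in 7.1 and Section 16, and footnote 9, point to a pre-dose form.

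**The case against.** The strongest reply is that 7.1 is explicit. It schedules day 26 for everyone and repeats the requirement after any early stop. Section 16 continues the questionnaire after termination, 9.6 has early stoppers seen as per the schedule, and the ±2 RT-day window in 9.6 around day 25 includes RT 26. This stands to the extent that the endpoint assessment is planned. A reader might infer that the trial never schedules its primary assessment, and 7.1 and Section 16 rule that out. But a reference to the study protocol does not say which section governs when sections disagree. The schedule that 9.6 points to is the one with the blank cell. And a window that can include RT 26 does not require a form then.

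A second reply concerns baseline. A reader might infer that the plan permits a post-dose baseline. Footnote 9 applies to that cell alone and says otherwise, so this is an ambiguity to settle, not a permission.

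Third, the wider on-drug range depends on reading the window in RT days. That is correct, so both readings are shown above. The on-drug problem is smaller in calendar days and absent for a Monday start.

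Fourth, the text of footnotes 11 and 12 and the treatment calendar (Appendix 30.1) are not in the supplied text, and the calendar may show day 26. That would ease the schedule point but would not repair 8.2, 9.6 or the windows.

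**Conclusion.** The conflict is real and should be fixed. Sections 16 and 7.1 make RT day 26 the primary time point. The Section 26 FACIT-F row, 9.6 and 8.2 do not name it, and footnote 6 names 27 questions where Section 1.3 defines a 40-item total (27+13). The day-26 window admits on-drug scores at IP days 11-14 (RT-day unit) or 13-14 (calendar unit), assuming one fraction per weekday and none missed. It also overlaps day 25 with no rule for choosing between forms.

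A reader might go on to infer a bias for or against dexamethasone, or a definite loss of power. The documents support neither. They give no rate of missing or mistimed forms and no figure for how the score changes around the last dose. The 10% allowance covers "up to a 10% drop-out of patients from their radiation therapy between days 16 and 26", which is a different loss. The nominal design is sound: with no missed fraction, RT day 26 is the day after the last dose for every starting weekday.

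**What to change.** 1. Mark RTD26 in the Section 26 FACIT-F row, and make footnote 6 read 40 items (27+13).
2. Add RT day 26 to 9.6 and to the RPG-stop sentence in 8.2, matching 7.1, and let the existing phone option in 9.6 cover it.
3. State the window unit once. RT days is the unit already used in footnote 6 and 9.6. Set the baseline at RT day 15 with window 0 to -2, always before the first IP dose.
4. Set the endpoint at RT day 26 with window 0 to +2, not before the day after the 14-day IP period. If IP is re-started under 8.2, count the 14 days from the re-start; if they end after RT day 26, open the window on the next RT day. The primary value is the first FACIT-F in the window, whatever its visit label, regardless of early IP stop.

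The cost is wording in 7.1, 8.2, 9.6, Section 16 and footnote 6, and one survey cell on a day already marked for the observation form. Each window narrows from five RT days to three if the unit is RT days. No patients are added.

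Two things remain outside this fix. IP continues through RT breaks (8.3), so one fraction missed after IP start moves RT day 26 to IP day 16, or 18 for a Friday start. A patient who leaves RT before day 26 still has no endpoint day and falls under the 10% allowance.

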## 1. INTRODUCTION

### 1.1 Phase:

This is a phase II, single center, randomized, double-blind, placebo-controlled study assessing the effects of dexamethasone versus placebo on radiation fatigue, quality of life (QoL), and treatment interruption in patients receiving definitive treatment for head and neck and non-small cell lung cancers. Subjects will be stratified by treatment (radiation alone vs. radiation plus systemic therapy) and randomized within strata to one of two treatment arms with equal probability.

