## **7. STUDY PLAN**

### **7.1 Treatment Regimen**

Subjects will be stratified by type of disease and whether or not they will be receiving chemotherapy and then randomly assigned to receive either dexamethasone 4 mg twice daily or placebo twice daily for 14 days via the oral route. Assignment of IP will be done in a double-blinded fashion. Both active drug and placebo will be compounded to look identical in appearance. Treatment with IP will start on day 16 of RT and subjects will complete a pill diary in order to track their medication adherence. Subjects will be advised to take the IP with food at approximately 8 a.m. and 2 p.m.  $\pm 2$  hours. Subjects will also be advised that if they are experiencing difficulty swallowing as a result of treatment and are unable to swallow a pill, they can mix the contents of the capsule with either applesauce or any liquid. They will also be asked to complete an observation form, beginning with their first day of IP and continuing until 60 days post RT, describing any side effects or problems they experience while on the study medication.

Subject's RPG levels will be monitored prior to starting IP via glucometer on RT days 15 [ $\pm 2$  days], 20 [ $\pm 2$  days] and 25 [ $\pm 2$  days], with optional testing per physician discretion on the final day of RT and 30 and 60 day RT follow-up visits. If subjects have had blood drawn within the  $\pm 2$  day window that includes glucose testing, they will not be required to have a fingerstick blood glucose test. Subjects who meet a modified Common Terminology Criteria Version 4.0 for adverse events Grade 3 hyperglycemia criteria, RPG level greater than or equal

to 250 mg/dL, will be told to discontinue IP immediately and have a repeat RPG level performed in 3 RT days.

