### **17.3 Interim Analysis**

An interim analysis for futility will be performed when 18 patients per group have completed their radiation therapy treatment. A conditional power analysis will be performed based on the data accumulated to date. Briefly, the observed results will be used to generate predicted results for future patients (assuming a normal distribution) with the observed mean and standard deviation observed in each group. One thousand bootstrap samples with a sample size of 36 patients per group (target sample size) will be generated to estimate conditional power. The study will continue if the conditional power is  $> 80\%$ . Note that this analysis is for futility only, so will not affect the overall alpha level.

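### The primary t test on change scores is valid but adjusts for neither the day-15 score nor the stratification factors; a prespecified ANCOVA could gain precision at almost no cost

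*Combined protocol and SAP*

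**What the plan says.** Section 16 defines the endpoint: "The primary outcome is the change in the fatigue score between radiation days 15 (day prior to IP initiation) and 26 (day after IP completion"). The analysis of this endpoint, and of change in the FACIT-F total score, "will be performed using a two-sample independent t test comparing the dexamethasone versus placebo patients". The test is one-sided ("We chose a one-sided statistical test (at the alpha = 0.05 level")), and the plan states that "36 patients per group will provide 80% statistical power", raised to 40 for drop-out. No covariate is named. Sections 16 and 17 contain no regression, ANCOVA or stratified analysis, and the exploratory work consists of by-arm profiles and descriptive statistics.

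The same section says "Randomization will be stratified by tumor location and treatment type (radiation alone versus radiation plus systemic therapy"). The other statements of the strata do not all agree with it:

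- Section 1.1 gives one factor: "Subjects will be stratified by treatment (radiation alone vs. radiation plus systemic therapy) and randomized within strata".
- The schema in Section 2 shows both tumour site and treatment type.
- Section 7.1 also has two factors but words the second differently: "Subjects will be stratified by type of disease and whether or not they will be receiving chemotherapy".

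Section 17.3 projects future patients from normal distributions "with the observed mean and standard deviation observed in each group", that is, from the arm-level summary of the outcome alone.

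**The concern.** A t test on change scores is an ANCOVA with the slope on the day-15 score fixed at 1 and the strata left out. If the true slope is below 1, as it is whenever the two scores have similar SDs and are imperfectly correlated, the change score carries avoidable day-15 noise. If the stratification factors predict change, stratified randomisation has already balanced them, yet the t test still counts their variation as error. Its standard error is then too large and the test is conservative.

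The design has 80% power only if drop-out stays within the 10% allowance, so free precision is worth having. The choice of model also has to be fixed in advance. Selecting between adjusted and unadjusted results after seeing the data would undermine a one-sided 0.05 test.

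**Working it through.** **Inputs from Section 16.** Mean improvement 9.0 (SD 10.30) on dexamethasone and 3.1 (SD 9.59) on placebo; one-sided alpha 0.05; 36 evaluable and 40 enrolled per group.

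**Inputs the documents do not give (assumptions).** rho, the correlation between day-15 and day-26 scores; k = SD at day 26 / SD at day 15; R², the share of change-score variance explained by the strata.

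**1. The plan's own figure.** Difference = 9.0 − 3.1 = 5.9. Pooled SD of change = √((10.30² + 9.59²)/2) = 9.951. At 36 per group the noncentrality is 5.9 / (9.951 × √(2/36)) = 2.515 on 70 df, with critical value 1.667. Power is 80.1%, and 36 is the smallest n that reaches 80%. Then 36/0.9 = 40. The plan's figures reproduce. If all 40 are evaluable, power is 83.7%.

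**2. Adjusting for the day-15 score.** In units of the day-15 variance, the change score has variance 1 + k² − 2·rho·k, and the ANCOVA residual has k²(1 − rho²). Their ratio is

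ratio = k²(1 − rho²) / (1 + k² − 2·rho·k).

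At k = 1 this is (1 + rho)/2. The denominator minus the numerator is (1 − rho·k)², so the ratio never exceeds 1. It equals 1 only when rho·k = 1, for example k = 1.25 with rho = 0.8.

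Power at 36 per group, holding the SD of change at 9.951 and giving up 3 df (day-15 score and two binary strata), against 80.1% unadjusted:

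| k | rho 0.3 | 0.5 | 0.7 | 0.8 | 0.9 |
|---|---|---|---|---|---|
| 1 | 92.6% | 89.1% | 85.4% | 83.6% | 81.9% |
| 1.25 | 87.8% | 83.9% | 80.8% | 80.1% | 81.9% |
| 0.8 | 96.9% | 95.0% | 93.3% | 92.9% | 93.9% |

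At 40 per group with k = 1 and rho = 0.5, power is 91.8% against 83.7%.

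**3. Adjusting for the strata alone.** If balanced strata explain a share R² of change variance, the true one-sided level of the t test is P(t70 > 1.667/√(1 − R²)).

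| R² | True level of t test | Power, t test | Power, strata-adjusted |
|---|---|---|---|
| 5% | 0.046 | 80.7% | 81.9% |
| 10% | 0.042 | 81.4% | 83.6% |

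**4. Simulation check.** 20,000 trials per setting, 36 per arm.

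| Setting | t test | ANCOVA |
|---|---|---|
| Power, k = 1, rho 0.5 | 79.8% | 88.8% |
| Power, k = 1.25, rho 0.5 | 79.9% | 83.4% |
| Power, k = 1.25, rho 0.8, no stratum effect | 79.9% | 79.3% |
| Type I error, R² = 10% | 0.042 | 0.051 |

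The simulated ANCOVA powers fall 0.3 to 0.8 points below the formula, which leaves out chance imbalance in the day-15 score. The third row is the least favourable case examined, a loss of about 0.6 points.

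**The case against.** The strongest reply is that nothing is broken. The t test is unbiased under randomisation, its sample size reproduces, and replacing one valid prespecified test with another is a preference. That is right about validity, and it is why this is an efficiency point.

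The size of the gain is also assumed. The 17-point end needs scores less variable at day 26 than at day 15 and only weakly correlated (k = 0.8, rho = 0.3), and nothing in the documents supports that corner. At rho of 0.7 to 0.9 with k of 1 or 1.25, the gain is about 0 to 5 points. This stands: no single figure should be promised. It does not remove the case for adjusting, because the downside is about half a point. The conservatism of the t test under prognostic strata is likewise mild and, taken alone, harmless.

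The covariate and outcome are not perfectly defined either. Section 7.1 allows ±2 days around day 15 while study drug starts on RT day 16, although footnote 9 in Section 26 puts that survey on the day before. The Section 26 schedule, as printed, has no FACIT-F mark at RT day 26. Both points need tidying, but they affect the planned change score just as much as an ANCOVA.

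Finally, all power figures here are for the final test alone. They ignore the futility rule in Section 17.3, whose effect on overall power is a separate matter.

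**Conclusion.** The point holds as an efficiency improvement that should be made. The planned test is valid and its 36 and 40 per group are correct. With the same patients, ANCOVA moves power at 36 per group from 80.1% to between roughly 80% and 97% over rho 0.3 to 0.9 and k 0.8 to 1.25. With equal SDs (k = 1) the range is 81.9% to 92.6%. The gain rests on rho and k, which the documents do not give, and it may be nil. The strata alone would add about 1 to 2 points if they explain 5% to 10% of change variance, and adjusting for them would bring the test back to its nominal level. The disagreement over which factors are strata is real and needs settling whichever analysis is used.

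**What to change.** Make these changes before anyone sees outcome data by arm, including at the interim look:

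1. **Section 16, primary analysis.** Specify ANCOVA of the day-26 FACIT-F fatigue subscale on arm, day-15 score, tumour site and treatment type, main effects only, with the arm effect tested one-sided at 0.05. Use the same model for the FACIT-F total score. Keep the change-score t test as a named sensitivity analysis.
2. **Strata.** Reconcile Section 1.1 with the schema, Section 7.1 and Section 16 on whether tumour site is a factor, and settle whether the second factor is chemotherapy or any systemic therapy. The model must use the factors actually used to randomise.
3. **Section 17.3.** Simulate day-15 and day-26 scores jointly for future patients, state how their strata are drawn (for example, in the proportions seen so far), and analyse each simulated trial with the same ANCOVA.
4. **Sample size.** Leave it at 40 per group, since the gain is unknown.

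The cost is wording in Sections 1.1, 7.1, 16 and 17.3, a modest change to the futility code, and 3 degrees of freedom. No new data and no extra patients are needed.

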#### Secondary

- QoL score assessed via the FACIT-F 40-item total score (27+13)
- Total days and cause of treatment interruption

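### The treatment-interruption comparison leaves the randomisation strata out and does not say which of two tests is the main result; one stratified Wilcoxon test would be clearer and at least as powerful.

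*Combined protocol and SAP*

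**What the plan says.** Section 1.3 lists the secondary endpoint as "Total days and cause of treatment interruption". The proportion of patients with any interruption is not a listed endpoint.

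For this endpoint Section 16 states: "Analysis of the total days of treatment interruption will be performed using a Wilcoxon Rank Sum Test", on the ground that days may not be normally distributed. The next sentence reads: "Alternatively, the proportion of patients with any treatment interruptions will be compared using a Fisher's Exact Test". It gives no trigger for the alternative and labels neither test as main or supportive. Section 17 adds nothing on the point.

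On the design, Section 16 states: "Randomization will be stratified by tumor location and treatment type (radiation alone versus radiation plus systemic therapy"). The schema and Section 7.1 also use disease site and systemic therapy. Section 1.1 names treatment type only and says subjects are "randomized within strata to one of two treatment arms with equal probability". Neither interruption test uses any of these factors.

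The only significance level in the plan sits in the sample-size paragraph and is argued from fatigue: "We chose a one-sided statistical test (at the alpha = 0.05 level) as dexamethasone will only be recommended in our patient population if it" improves that symptom. No alpha or sidedness is given for interruption.

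**The concern.** There are two separate weaknesses.

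First, the two tests answer different questions. The Wilcoxon test uses how many days were lost. Fisher's test uses only whether any were lost, so it is nearly blind to a drug that shortens interruptions without preventing them. With no stated order, the reported result is not fully fixed in advance.

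Second, stratified randomisation balances the arms within strata. If strata differ in interruption risk, part of the patient-to-patient variation can no longer contribute to the difference between arms. An unstratified test still counts that variation in its standard error. It then rejects too rarely under no effect and misses real effects more often.

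Interruption appears in the study description (Section 1.1), the secondary objective (Section 3.2) and the hypothesis (Section 4.1), which also links it to loco-regional control and survival. Power lost here has no offsetting benefit.

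**Working it through.** **The plan's own figure.** The only sample-size calculation concerns fatigue. The mean difference is 9.0 − 3.1 = 5.9. The pooled variance is (10.30² + 9.59²)/2 = 99.03, so the SD is 9.951. With one-sided alpha 0.05 and 80% power, n = 2 × (1.645 + 0.842)² × 99.03 / 5.9² = 35.2, hence 36 per group, and 36/0.9 = 40 with drop-out. The stated figures reproduce. Nothing comparable exists for interruption, so every rate below is an assumption.

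**Why the unstratified tests are conservative: a hand check.** Take four equal strata, exactly balanced by arm, and the indicator of any interruption. The unstratified test uses the total variance p̄(1 − p̄), but the difference between arms varies only with the mean within-stratum variance.

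- Rates 10/30/30/50%: total 0.30 × 0.70 = 0.210; within (0.09 + 0.21 + 0.21 + 0.25)/4 = 0.190. The SD ratio is √(0.190/0.210) = 0.951. A cut-off of 1.96 acts like 1.96/0.951 = 2.06, a true two-sided error of 3.9%.
- Rates 5/20/40/70%: total 0.3375 × 0.6625 = 0.2236; within (0.0475 + 0.16 + 0.24 + 0.21)/4 = 0.1644. The ratio is 0.857, the effective cut-off 2.29, and the true error 2.2%.

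Simulation of the actual tests on days (20,000 null trials each, 40 per arm, two-sided 5%) agrees:

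| Stratum rates | Wilcoxon | Fisher | Either significant | van Elteren |
|---|---|---|---|---|
| 10/30/30/50% | 3.9% | 2.0% | 3.9% | 4.9% |
| 5/20/40/70% | 2.1% | 0.9% | 2.2% | 4.8% |
| 60/70/80/90% | 4.5% | 2.3% | 5.8% | 5.1% |

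A more extreme contrast (5/5/80/80%) took the Wilcoxon down to 0.4%.

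**Power.** Four scenarios, one-sided 5%, 40 per arm, geometric days when interrupted. The order is head and neck RT alone, head and neck systemic, lung RT alone, lung systemic.

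| Per-arm stratum sizes | Control rate of any interruption |
|---|---|
| 6/20/4/10 | 15/70/10/50% |
| 10/10/10/10 | 15/70/10/60% |
| 4/26/2/8 | 30/50/25/40% |
| 2/29/1/8 | 20/60/20/50% |

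Rejection rates, as ranges over the four scenarios and repeat simulations:

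| Situation | Wilcoxon | Fisher | van Elteren |
|---|---|---|---|
| No effect | 2.2–5.3% | 0.8–2.8% | 4.6–5.7% |
| Odds ratio 0.4 on any interruption, mean days 4 to 2.5 | 48–75% | 29–52% | 60–76% |
| Shorter interruptions only, mean days 5 to 2.5 | 9–24% | 1–3% | 16–29% |

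In the second row, the gain of van Elteren over Wilcoxon within a scenario is 0.4 to 13 points. It is near zero when strata differ little. No scenario showed a loss.

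**Effect of free choice.** Suppose the analyst reports whichever named test is significant.

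- Identical strata: error is 4.6% to 5.4% at interruption rates of 10% to 30%, 5.5% to 5.8% at 50%, and 6.0% to 6.6% at 70% to 90%. Two independent tests would give 1 − 0.95² = 9.75%; these two are strongly correlated.
- Differing strata: about 2% to 6%. In the four power scenarios, Fisher was significant without Wilcoxon in at most about 0.5% of null trials.
- Real effect (second row): the two tests disagreed on significance in 19% to 26% of trials, nearly always with Wilcoxon significant and Fisher not.

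**The case against.** A reader might infer that the open choice inflates the false-positive rate above a nominal 5%. The documents do not support that. They set no level for this endpoint, since the one-sided 0.05 is tied to fatigue. The computed inflation is at most about 1.6 points (6.6 − 5.0) with identical strata, and with differing strata the error is mostly below 5%.

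A reader might also infer that two analysts could reach opposite conclusions. The disagreement is a power gap: one test is significant and a weaker one, on a different summary, is not. The directions do not conflict.

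Nor is a choice after seeing the data a certainty. The Wilcoxon test is named first, without condition and with a reason, and it alone matches the listed endpoint. A reasonable reader would take it as the main test. What stands is that the plan does not say so.

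On the strata, the unstratified tests do not produce excess false positives, and the documents give no evidence that interruption risk differs between strata. The simulations also assume exact balance within every stratum, while Section 9.2 mentions blocks without a size. Where allocation was not balanced within strata, the Wilcoxon error returned to 4.7% to 5.1%, so the loss shrinks as balance weakens. These points limit the size of the gain. They give no reason to prefer the unstratified tests, because the stratified one lost no power in any scenario.

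**Conclusion.** The point holds as an efficiency and clarity improvement on a secondary endpoint. The plan stratifies the randomisation, leaves the strata out of both interruption tests, and does not say which test is the main result. If strata differ in risk, both tests are conservative. A single van Elteren test would hold about 5% error and gain roughly 0 to 13 points of power over the Wilcoxon. The Wilcoxon is itself about 19 to 26 points above Fisher in the assumed-effect scenarios, because the disagreements run almost entirely one way.

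These sizes rest on assumed interruption rates, interruption lengths, stratum sizes and effects, on 40 patients per arm, and on near-exact balance within strata. The direction depends only on strata differing in risk and on balanced allocation within them. The primary FACIT-F analysis is outside this point.

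**What to change.** Replace the two interruption sentences in Section 16 with wording such as:

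> Total days of treatment interruption will be compared with one van Elteren (stratified Wilcoxon) test, stratified by the randomisation factors actually used. The proportion with any interruption will be reported per arm with a Mantel-Haenszel stratified difference and confidence interval, as supportive only.

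Add the alpha and sidedness for this endpoint. If the one-sided 0.05 argued for fatigue is meant to apply here, say so and give the reason.

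Reconcile Section 1.1 (treatment type only) with the schema and Sections 7.1 and 16 (disease site and treatment type), so that the stratification in the test matches the randomisation.

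The cost is wording only: no new data, visits or patients. The change should be made before unblinding.
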